date (i.e., similar to the matched oxygen therapy patient in time from the fibrosing ILD diagnosis date to the index date, and during the same continuous enrollment period as the fibrosing ILD diagnosis date).

NOTE: Following review of results from Aim 1, the study team will determine whether continuous enrollment criteria for Aim 2 and Further Aim requires revision.

Variables:	
Aim 1
 
Outcomes: time to initiation of oxygen therapy; time to sustained oxygen therapy use; sustained oxygen therapy use within the first 12 months of follow-up
 
Baseline covariates: demographic characteristics (age, sex, race/ethnicity, geographic region, insurance type, index year), clinical characteristics (underlying ILD type; respiratory diseases; other clinical characteristics; Quan-Charlson comorbidity score; Agency for Health Research and Quality [AHRQ] comorbid conditions; smoking; pulmonary rehabilitation) healthcare utilization characteristics (provider specialty; medication use; all-cause HCRU; all-cause health care costs)
 
Stratification: IPF vs non-IPF ILD
 
Aim 2 [REDACTED]
 
Exposure: oxygen therapy vs no oxygen therapy
 
Primary Outcomes: Time to disease progression; time to all-cause mortality; time to hypoxemia, time to acute exacerbations, counts of acute exacerbations
 
[REDACTED]
 
Baseline covariates: demographic characteristics (index year, age, sex, race/ethnicity, geographic region, insurance type), clinical characteristics (underlying ILD type; respiratory diseases; other clinical characteristics; Quan-Charlson comorbidity score; AHRQ comorbid conditions; smoking; pulmonary rehabilitation) healthcare utilization characteristics (provider specialty; medication use; all-cause HCRU; all-cause health care costs)

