5. RATIONALE AND BACKGROUND

Interstitial lung disease (ILD) is a broad term that describes more than 200 diverse lung disorders, including idiopathic pulmonary fibrosis (IPF), autoimmune ILD, hypersensitivity pneumonitis (HP), and sarcoidosis.¹ Typical symptoms of ILD include cough and dyspnea, as well as decreased lung capacity², which leads to exercise intolerance and hypoxemia.

The major goal of therapy in ILD patients is to slow disease progression as well as improve the associated dyspnea, exercise capacity, and health-related quality of life.³ Approved treatment options for fibrosing ILD comprise antifibrotic treatments including nintedanib and pirfenidone, which slow the rate of decline in forced vital capacity (FVC). Other commonly prescribed treatment options are corticosteroids, immunosuppressants, opioids, and lung transplantation.⁴ Despite advances in pharmacotherapy, many patients continue with disease progression. Oxygen therapy is commonly administered to reduce breathlessness and increase physical capacity by improving gas exchange.⁵

Supplemental oxygen (O₂) is commonly prescribed in clinical practice for patients with fibrotic ILD; however, robust evidence to support its long-term use is lacking. Recommendations for long-term oxygen therapy (LTOT) for resting hypoxemia in ILD are largely extrapolated from trials conducted in chronic obstructive pulmonary disease (COPD), where a survival benefit is well established.^{6,7} The American Association for Respiratory Care guideline recommends the use of oxygen therapy to maintain the oxygen saturation (SpO₂) range of 94–98% for most hospitalized patients.⁸ Despite its frequent use, there is a paucity of studies evaluating the incidence, prevalence, and impact of LTOT on outcomes such as disease progression or mortality in ILD. This study will help fill in the gaps in increasing the understanding of the use of oxygen therapy among fibrosing ILD patients and assess whether the use of oxygen leads to better or worse outcomes.

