7.3.3.2 Secondary Outcomes

- **Hypoxemia**—Sample size permitting, hypoxemia (i.e., oxygen saturation [SpO₂] <90%) will be captured as available in the database using specific ICD-10-CM codes or EHR data among the subset of patients with both claims and EHR in the Market Clarity database. Time to hypoxemia will be reported as time between index date and first evidence of hypoxemia.
- **Respiratory deterioration/Acute exacerbations**—An acute exacerbation of fibrosing ILD has been defined clinically as an unexplained worsening or development of dyspnea within 30 days in combination with a high-resolution CT indicating interstitial pneumonia, and excluding pulmonary infection, left heart failure, pulmonary embolism or other identifiable causes of acute lung injury.⁹ Based on these clinical criteria, acute exacerbations will be defined as follows:
 - ≥1 claim with procedure code for CT scan, and
 - Evidence of dyspnea, as defined by ICD-10-CM codes or EHR data in the integrated database, within 30 days prior to date of CT scan, and
 - No claims with diagnosis for pulmonary infection, left heart failure, pulmonary embolism, or other identifiable causes of acute lung injury within 30 days prior to date of CT scan.

The time to first exacerbation and population annualized counts of exacerbations (sum of all exacerbations for all individuals / sum of follow-up time [person years] for all individuals) will be described. Exacerbations occurring within 14 days of each other will be considered a single exacerbation episode. The start date of the exacerbation episode will be the service date of the first event (i.e., dyspnea or CT scan). The end date of the exacerbation episode will be defined as the last observed exacerbation event date (or discharge date if event occurs during an inpatient stay) + 14 days. Exacerbation episodes that include an inpatient stay will also be reported separately as exacerbations involving a hospitalization.

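### The acute-exacerbation rule in 7.3.3.2 drops the worsening of dyspnea and the CT finding from the definition it cites, so a stable patient with chronic dyspnea and a scheduled CT can count as an event

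*Combined protocol and SAP*

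**What the plan says.** Section 7.3.3.2 opens with a clinical definition of acute exacerbation: "unexplained worsening or development of dyspnea within 30 days in combination with a high-resolution CT indicating interstitial pneumonia", with infection, left heart failure, pulmonary embolism and other identifiable causes excluded. It presents its working rule as derived from these criteria. The rule has three conditions, all required:

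- "≥1 claim with procedure code for CT scan"
- "Evidence of dyspnea, as defined by ICD-10-CM codes or EHR data in the integrated database, within 30 days prior to date of CT scan"
- "No claims with diagnosis for pulmonary infection, left heart failure, pulmonary embolism, or other identifiable causes of acute lung injury within 30 days prior" to the CT date.

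On repeated events: "Exacerbations occurring within 14 days of each other will be considered a single exacerbation episode". An episode starts on the date of its first event, whether that is the dyspnea or the CT. Time to first exacerbation and a count per person-year are reported on this rule. The section adds: "Exacerbation episodes that include an inpatient stay will also be reported separately as exacerbations involving a hospitalization".

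Section 5, like the abstract, states: "Typical symptoms of ILD include cough and dyspnea". Section 7.1 says exacerbations in the Aim 2 follow-up will be compared between the matched cohorts. The abstract lists "time to hypoxemia, time to acute exacerbations, counts of acute exacerbations" among the Aim 2 primary outcomes, whereas the body places them under secondary outcomes.

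**The concern.** What makes the clinical event acute is a change in dyspnea together with a CT finding. The working rule asks only that dyspnea be on record and that a scan be billed. In a disease where dyspnea is usual, those two facts can coincide at a planned imaging visit.

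The outcome then partly measures how often dyspnea is written down and how often CT is ordered. It is meant to compare patients who start oxygen with patients who have not. The protocol says oxygen is given to reduce breathlessness, so one component of the outcome is also a reason for the exposure, and dyspnea records can be expected around the index date. The text does not say that the qualifying dyspnea record must fall on or after index. As written, a CT soon after index could pair with the dyspnea that led to the oxygen prescription. Because an episode starts at its first event, such an episode would even start before follow-up does. A difference between cohorts, or the lack of one, could not then be read as a statement about acute exacerbations.

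**Working it through.** **Step 1: compare the definition with the rule (both in 7.3.3.2).**

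| Element | Clinical definition cited | Working rule | Kept? |
|---|---|---|---|
| Dyspnea | New or worsening, within 30 days | Any record in the 30 days before CT | Window kept, change dropped |
| CT | High-resolution, indicating interstitial pneumonia | A procedure code | Finding dropped |
| Other causes | Excluded | No such diagnosis claim in the prior 30 days | Kept |

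The text has no dyspnea-free look-back and no care-setting requirement. A stable patient with chronic dyspnea on record, none of the excluded diagnoses and a scheduled CT within 30 days satisfies all three conditions.

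**Step 2: check the safeguards.** The exclusions remove visits with a coded alternative cause; they do nothing for a stable patient without one. The 14-day merge limits repeat counting but does not separate stable from acute visits. The hospitalized report is a subset shown in addition; the time-to-event and count outcomes do not require it.

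**Step 3: size.** The plan gives no exacerbation rate, predictive value or power figure for this outcome, so there is nothing to reproduce. Every input below is an assumption, used only to show how the error behaves.

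- c = routine CTs per person-year: 0.5 to 2
- d = chance of a dyspnea record in the prior 30 days: 0.2 to 0.8
- x = chance of an excluding diagnosis: 0.1 to 0.5
- t = true exacerbations per person-year: 0.05 to 0.20

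False episodes per person-year: f = c × d × (1 − x).

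- Lowest: 0.5 × 0.2 × 0.5 = 0.05
- Middle: 1 × 0.5 × 0.7 = 0.35
- Highest: 2 × 0.8 × 0.9 = 1.44

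Share of counted events that are true: t / (t + f).

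- Middle f: 0.05/0.40 = 0.13 to 0.20/0.55 = 0.36
- Full range: 0.05/1.49 = 0.03 to 0.20/0.25 = 0.80

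Same false rate in both cohorts: observed ratio = (RR × t + f) / (t + f). With f = 0.35:

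- True 0.70 appears as (0.14 + 0.35)/0.55 = 0.89 when t = 0.20, and (0.035 + 0.35)/0.40 = 0.96 when t = 0.05
- True 1.50 appears as (0.30 + 0.35)/0.55 = 1.18 and (0.075 + 0.35)/0.40 = 1.06
- True 1.0 stays at 1.0

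False rate k times higher in the oxygen cohort, true ratio 1.0: observed ratio = (t + k × f) / (t + f). With f = 0.35:

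- k = 1.25, t = 0.20: 0.6375/0.55 = 1.16
- k = 2, t = 0.05: 0.75/0.40 = 1.88

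If the no-oxygen cohort has the higher false rate instead, the ratios invert: 1/1.16 = 0.86 and 1/1.88 = 0.53.

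**The case against.** The defense has real substance.

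- **The rule has a third condition.** A reader might infer that any dyspnea record plus any CT is enough. It is not: the exclusion diagnoses carry over a genuine part of the clinical definition. They do not, however, restore acuity.
- **The CT codes are not visible.** The contents of Annex 4 are not in the public text, and Section 7.7 says code lists are built and reviewed by clinical coding experts. They may restrict CT to chest or high-resolution codes, so it cannot be said that a CT of any kind qualifies. A procedure code would still show neither the finding nor the reason for the scan.
- **Repeat scans often merge.** A reader might infer that a second CT a few weeks later is a second event. With CTs on days 0 and 21 and dyspnea recorded on day 10, the second event starts on day 10 and merges with the first. Separate counting needs the second event's qualifying dyspnea to fall more than 14 days after the first episode's events.
- **The direction of bias is not established.** A reader might infer that oxygen users will show excess exacerbations. For example, with 0.10 true events per year in each cohort, 1.5 versus 1.0 non-acute CTs per year and 40% of those qualifying, the counts are 0.10 + 0.60 = 0.70 and 0.10 + 0.40 = 0.50, a ratio of 1.4. That ratio comes wholly from the assumed difference in CT rates; with equal rates it is 1.0. Prior utilization and provider specialty are among the baseline covariates, and matching on them may balance earlier care intensity, though it does not equalize recording and imaging after index.
- **The Aim 2 analysis is not visible.** Section 7.2.3 points to Section 7.6.2.2, which is not in the public text. How the hospitalized version is used there, and whether a sensitivity analysis exists, cannot be judged.
- **The plan signals some breadth.** The outcome carries the heading of respiratory deterioration as well as acute exacerbation, and the limitations section mentions coding error, though only in general terms.

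These points narrow the claim. None of them puts new or worsening dyspnea, or a CT finding, back into the rule.

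**Conclusion.** The point holds in this form: the rule omits the change in dyspnea and the CT finding, and so admits stable patients with chronic dyspnea, a scheduled CT and no excluding code. That follows from the text of 7.3.3.2 and Section 5 and needs no assumption. It affects the time to first exacerbation and the annualized counts, which are to be compared between cohorts.

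The size is unknown. Under the assumed inputs, the share of counted events that are true runs from 0.03 to 0.80, which is too wide to serve as an estimate. What can be said is the pattern: equal false events shrink a true effect toward 1, and unequal ones can create or reverse an effect in either direction. The documents do not support a specific biased ratio, nor a claim that most counted events are false. The change should be made before the comparison is run.

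**What to change.** In 7.3.3.2:

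1. Prespecify the between-cohort comparison, both time to first event and annualized counts, on episodes whose qualifying dyspnea and CT are tied to an inpatient stay or an emergency visit. State the permitted gap in days between those records and the encounter.
2. Require the qualifying dyspnea record to fall on or after the index date.
3. Report the broad CT-plus-dyspnea version as a sensitivity analysis labelled respiratory deterioration.

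The cost is wording and programming. Section 7.3.5.3 already defines inpatient admissions and emergency visits, Section 7.1 includes utilization in the Aim 2 follow-up, and the hospitalized subset is already to be built.

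There are downsides. The cited clinical definition has no hospital requirement, so the acute encounter is a stand-in for acuity and not a restoration of the missing elements. Exacerbations managed only in outpatient care would appear only in the sensitivity analysis. Encounter rates may also differ between cohorts, so bias from care intensity is reduced but not removed.

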7.3 VARIABLES

Variables related to the study period will be defined as follows:

Aim 1

- **Fibrosing ILD diagnosis date**—The first ILD diagnosis date for patients with ≥ 2 fibrosing ILD diagnoses on different dates and within 365 days. The fibrosing ILD diagnosis date is the first day of follow-up observation time for Aim 1.
- **Pre-ILD baseline period**—The 12-month period prior to the fibrosing ILD diagnosis date.
- **Aim 1 follow-up period**—The variable period starting on the fibrosing ILD diagnosis date and continuing until the earliest of the following: disenrollment from the health plan, death, or end of the study period. The Aim 1 follow-up period will be used to assess Aim 1 outcomes.
 - **All-cause mortality**—Death will be used as a censoring event and is further defined in Section 7.3.3.1.

Aim 2

- **Index date**—For the oxygen therapy cohort, the first date following the fibrosing ILD diagnosis date with a claim with diagnosis for oxygen therapy; for the no oxygen therapy cohort, a date within the same continuous enrollment period as the fibrosing ILD diagnosis date that is similar to the matched oxygen therapy patient in time from fibrosing ILD to index date. The index date is the first day of follow-up observation time for Aim 2 and Further Aim.
- **Pre-index baseline period**—The 12-month period prior to the index date.
- **Aim 2 follow-up period**—The variable period starting on the index date until the earliest of the following: disenrollment from the health plan, death, or the end of the study period. Matched pairs will be given the same duration of follow-up. The Aim 2 follow-up period will be used to assess Aim 2 and Further Aim outcomes.
 - **All-cause mortality**—Death will be used as a censoring event and is further defined in Section 7.3.3.1.

An overview of the analytic study variables and the study periods for which each analytic variable will be reported is provided in Table 1. Additional variable information is provided in Sections 7.3.1 to 7.3.4.

Table 1. Analytic Variables by Data Source and Time Period

Characteristic	Data source		Aim 1 time period		Aim 2 time period	
	Claims*	EHR	Pre-ILD baseline	Follow-up	Pre-index baseline	Follow-up
Aim 1 outcomes						
Oxygen therapy (time to initiation, sustained oxygen therapy use)		X		X	X	
Aim 2 outcomes						
Disease progression	X	X				X
All-cause mortality	X					X
Hypoxemia	X	X	X		X	X
Acute exacerbations	X	X				X
Patient characteristics†						
Index year	X		X		X	

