7.8 LIMITATIONS OF THE RESEARCH METHODS

This study should be considered in the context of its limitations. First, identification of patients with newly diagnosed fibrosing ILD will rely on application of a claims-based algorithm. Presence of a diagnosis code does not necessarily indicate presence of disease; however, to limit misidentification of ILD patients, a confirmatory diagnosis will be required. Further, patients without ILD diagnosis in the 12-month baseline will be considered newly diagnosed. However, it is possible that patients with prevalent ILD who have not sought frequent care for their condition may be misclassified as newly diagnosed ILD patients.

Second, this study will utilize both claims and EHR data available in Optum's Market Clarity Integrated Claims + Clinical database to capture ILD symptoms, pulmonary function testing results, and hypoxemia. EHR data will be available for only a subset of the identified population; for remaining patients, these values will rely on information available in claims. Further, the analysis will rely on the availability of valid values (e.g., laboratory results) in the EHR data.

Third, all ILD patients included in this study were enrolled in a health plan (i.e., commercial, Medicare, or Medicaid) during the study period; thus, findings from this study may not be applicable to uninsured populations and patients with health plans not represented in the database.

Fourth, this study will minimize bias by utilizing propensity score matching on baseline variables (oxygen therapy versus no oxygen therapy cohorts) to examine outcomes of interest. Employing matching will enable a comparison of outcomes among patients who were similar on pre-ILD baseline characteristics. However, residual and/or unobserved confounding cannot be ruled out.

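### The acute-exacerbation rule accepts dyspnea from codes or EHR but excludes other causes on claims only, so a cause recorded only in the EHR leaves the event in the count

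*Combined protocol and SAP*

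**What the plan says.** Section 7.3.3.2 first gives a clinical definition of acute exacerbation: unexplained worsening with a supporting high-resolution CT, "excluding pulmonary infection, left heart failure, pulmonary embolism or other identifiable causes of acute lung injury". It then turns this into three data criteria, each with its own source:

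- CT: "≥1 claim with procedure code for CT scan, and"
- Dyspnea: "Evidence of dyspnea, as defined by ICD-10-CM codes or EHR data in the integrated database, within 30 days prior to date of CT scan"
- Other causes: "No claims with diagnosis for pulmonary infection, left heart failure, pulmonary embolism, or other identifiable causes of acute lung injury within 30 days prior" to the CT date

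Time to first exacerbation and annualized counts are reported. The abstract lists both among the Aim 2 primary outcomes, whereas the body places them under secondary outcomes in 7.3.3.2. Table 1 in Section 7.3 marks claims and EHR for the outcome as a whole ("Acute exacerbations X X"). Section 7.8 adds: "EHR data will be available for only a subset of the identified population; for remaining patients, these values will rely on information available in claims".

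**The concern.** The clinical definition removes events with another identifiable cause, and it does not limit where that cause may be recorded. The data rule consults the EHR to find the symptom but not to find the explanation. One EHR encounter that codes both dyspnea and pneumonia can supply the dyspnea, while its pneumonia is ignored unless it also reached a claim.

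Two things are at stake:

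- The count can include events whose other cause is visible in the study's own data. If such events arise at similar rates in both cohorts, they pull a relative comparison toward no difference.
- Patients with EHR data have an extra route into the event definition without the matching route out, so the rule depends on data availability. The hypoxemia outcome in the same section is limited to patients with both sources; the exacerbation outcome is not.

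**Working it through.** The plan gives no exacerbation rate, sample size or power for this outcome, so there is no figure to reproduce. The check is mainly a comparison of texts.

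**Step 1. Sources by criterion (7.3.3.2).**

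| Criterion | Effect on the count | Claims | EHR |
|---|---|---|---|
| CT | required | yes | not named |
| Dyspnea | creates an event | yes (ICD-10-CM codes) | yes |
| Other cause | removes an event | yes | not named |

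**Step 2. Does other text extend the exclusion to the EHR?**

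- Table 1 marks the EHR for the outcome without dividing it by criterion. The dyspnea criterion alone satisfies that mark.
- Section 7.8 names ILD symptoms, pulmonary function results and hypoxemia as the items drawn from both sources. It does not name the excluding diagnoses.
- Section 7.4 says the EHR holds coded diagnoses and laboratory results including microbiology, so the information is held.

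No visible text repairs the third criterion.

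**Step 3. Literal application when there is a CT claim and the other cause is absent from claims.**

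| Dyspnea found in | Other cause recorded in EHR only | Patient with EHR data | Same episode if no EHR data were held |
|---|---|---|---|
| Claims | yes | counted | counted (cause not visible) |
| EHR only | yes | counted | not counted |

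The first row is an error that could be avoided in patients with EHR data. The second row is the part that makes the rule more permissive in those patients.

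**Step 4. Illustration of size, in patients with EHR data.** Let q be the share of CT-plus-dyspnea events that have an excluding cause, and m the share of those causes recorded only in the EHR. Both are assumptions; the documents give neither. If claims catch the remaining causes,

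false share of counted events = q·m / (1 − q + q·m).

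For q = 0.5 and m = 0.20: 0.10 / (0.50 + 0.10) = 16.7%.

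| q | m = 0.02 | m = 0.05 | m = 0.10 | m = 0.20 |
|---|---|---|---|---|
| 0.3 | 0.8% | 2.1% | 4.1% | 7.9% |
| 0.5 | 2.0% | 4.8% | 9.1% | 16.7% |
| 0.7 | 4.5% | 10.4% | 18.9% | 31.8% |

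Two cautions apply. The table covers both rows of Step 3, so the part due strictly to the source mismatch (second row) is at most these values. It also applies only where EHR data exist. If a share e of counted events comes from such patients, the fix can remove at most e times the tabulated value. With e = 0.5 (an assumption), q = 0.5 and m = 0.20, that is 0.5 × 16.7% = 8.3%.

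**The case against.** The strongest reply is that the split is deliberate. Section 7.8 assigns symptoms to both sources; dyspnea is a symptom, while infection, embolism and heart failure are diagnoses that claims usually carry. Patients have medical coverage, follow-up ends at disenrollment, and the CT claim shows that the patient is generating claims at that time. Many treated causes would therefore also appear in claims, and m may be near the low end. This stands as a limit on size. It does not explain why a coded diagnosis held in the EHR should be ignored when the rule is said to rest on criteria that exclude it.

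A second reply is that a wider exclusion has its own cost. Section 7.3.5.2 lists heart failure as a baseline characteristic. Searching more records for it may remove true exacerbations in patients who already had it. This also stands, and the illustration above does not count it.

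A third reply is that Section 7.4 describes claims linked to EHR data, while 7.8 says "EHR data will be available for only a subset of the identified population", so the number of patients without EHR data is unclear. If nearly all have it, the unequal scoring shrinks, but the missed exclusions remain.

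A reader might also infer that the mismatch has a known cost: for example, if claims find 80% of causes and claims plus EHR find 95%, with half of candidate events having a cause, the false share falls from 16.7% to 4.8%. The arithmetic is right, but the documents do not support that reading. Neither capture rate is in the plan. The 16.7% measures what claims miss: it would be the same if dyspnea were also taken from claims only, with no mismatch left. The 4.8% credits the gain to every patient, although only those with EHR data can benefit.

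**Conclusion.** The point holds as a defect in the stated outcome rule. Followed literally, 7.3.3.2 keeps events whose other cause is recorded in the study's own EHR data, contrary to the definition it says it implements, and it scores patients differently according to whether EHR data exist.

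The size cannot be determined. The illustrative range of about 1% to 32% of counted events, in patients with EHR data, rests wholly on assumed q of 0.3 to 0.7 and m of 0.02 to 0.20. The true value may be small.

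A reader might infer that the rule biases the oxygen comparison, for instance because oxygen users have more EHR contact. The documents do not support this: they give no EHR coverage by cohort, and the matching procedure (7.6.2.2) is not in the public text, so whether it handles EHR availability cannot be judged. The correction is worth making because the outcome carries an Aim 2 comparison, listed as primary in the abstract and secondary in the body, and because the change is inexpensive.

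**What to change.** Reword the third criterion along these lines: *no claim diagnosis and no EHR encounter diagnosis, dated within the 30 days before the CT, for any of the listed excluding causes; carried-forward problem-list entries do not count.* This applies the same sources to the diagnosis-based criteria that create and remove events.

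Add a sensitivity analysis in which dyspnea and exclusions both come from claims only, in all patients. It scores patients with and without EHR data alike. It does not recover causes that claims miss, so it complements the rewording and does not replace it.

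The cost is one reworded bullet, one further lookup in data already linked, and one additional run. The event count will be somewhat smaller, and some true exacerbations may be excluded in patients with pre-existing heart failure. Reporting how many events the EHR search removes, by cause, would show how much of the reduction comes from heart failure.

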7.2.3 Study population: Aim 2 [REDACTED]

The analysis for Aim 2 and Further Aim will include patients identified for Aim 1 in Section 7.2.2 who meet the following additional selection criteria. Final oxygen therapy cohorts will be determined during the propensity score matching (PSM) procedure outlined in Section 7.6.2.2.

- **Oxygen therapy cohort**

- ILD patients with ≥ 1 medical claim for oxygen therapy after fibrosing ILD diagnosis. The ***index date*** will be defined as the first date of a claim for oxygen therapy.

- **No oxygen therapy cohort**
 - Matched to a patient in the oxygen therapy cohort. The **index date** will be assigned as a date that is eligible to set an index date (i.e., similar to the matched oxygen therapy patient in time from the fibrosing ILD diagnosis date to the index date, and during the same continuous enrollment period as the fibrosing ILD diagnosis date).

NOTE: Following review of results from Aim 1, the study team will determine whether criteria for Aim 2 and Further Aim require revision.

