7.3.3 Aim 2 Outcomes

7.3.3.1 Primary Outcomes

All primary outcomes will be measured in the Aim 2 and Further Aim follow-up period, unless specified otherwise.

- **Time to disease progression**—Pulmonary function test (PFT) results will be captured as available in the database in the pre-ILD baseline, pre-index baseline, and Aim 2 follow-up periods among the subset of patients who have EHR data during the same

time of ILD diagnosis and oxygen therapy. All valid result values will be captured. Values closest to the fibrosing ILD diagnosis date will be reported for the pre-ILD baseline period; values closest to the index date will be reported for the pre-index baseline period; the latest values prior to the end of follow-up will be reported for the Aim 2 follow-up period. PFT tests may potentially include forced expiratory volume in 1 second (FEV₁), forced vital capacity (FVC), FEV₁/FVC ratio, lung volumes, and diffusing capacity for carbon monoxide (DLCO), as available.

Among patients or matched pairs with FVC results in the pre-index and follow-up periods, disease progression will be defined as a 10% relative change between the pre-index value and the follow-up value. Time to disease progression will be reported. Additionally, time in days from pre-index FVC result to the index date and from index date to follow-up FVC result will be reported.

- **Time to all-cause mortality**—We will assign the date of death as the 15th day in the month of death. Time to all-cause mortality will be calculated as time between index date and mortality date.

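### The exacerbation definition does not separate events before oxygen start from events after it, so the deterioration that led to oxygen can be counted as an outcome of oxygen

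*Combined protocol and SAP*

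**What the plan says.** Section 7.3.3.2 builds an acute exacerbation from three parts: a CT claim; dyspnea found in coded diagnoses "or EHR data in the integrated database, within 30 days prior to date of CT scan"; plus the absence of any claim for a listed alternative cause in the same 30 days. The date rule is "The start date of the exacerbation episode will be the service date of the first event (i.e., dyspnea or CT scan". The merging rule is "Exacerbations occurring within 14 days of each other will be considered a single exacerbation episode". Two measures follow: time to first exacerbation, and a count divided by follow-up person-years.

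For the oxygen cohort, Section 7.2.3 says that the index date "will be defined as the first date of a claim for oxygen therapy". A comparator's index date is assigned so that time since fibrosing ILD diagnosis is similar. Section 7.3 adds: "The index date is the first day of follow-up observation time for Aim 2 and Further Aim", and "The Aim 2 follow-up period will be used to assess Aim 2 and Further Aim outcomes". Table 1 marks acute exacerbations for Aim 2 follow-up only.

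Section 7.3.3.1 has its own restriction, "All primary outcomes will be measured in the Aim 2 and Further Aim follow-up period, unless specified otherwise", but it is worded for primary outcomes. Section 7.3.3.2 places exacerbations among the secondary outcomes, while the abstract lists them as primary. Section 7.3.3.2 measures time to hypoxemia from the index date and gives no origin for time to first exacerbation.

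**The concern.** The event has two dated components up to 30 days apart, and the visible text does not say which one must lie in follow-up. It does not limit the dyspnea to the time after index, say what happens to an episode already under way at index, or stop the 14-day merging there.

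The abstract and Section 5 both name relief of breathlessness as a reason for giving oxygen. Dyspnea is therefore both a trigger for exposure and a component of the outcome. A comparator's index date has no such trigger. The covariates listed in Section 7.3.5 do not name dyspnea or a previous exacerbation.

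At stake is the Aim 2 comparison of exacerbations between matched cohorts. An episode that led to oxygen and is then credited to oxygen is reverse causation, and it would count against oxygen. The annualized count would also mix periods: its denominator is follow-up time, while its numerator could include episodes that began earlier.

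**Working it through.** The plan gives no event rate or other figure for this outcome, so there is nothing to reproduce. The check is day arithmetic.

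**Inputs.** Index is day 0 and belongs to follow-up (Section 7.3). The CT is on day c and the dyspnea on day d, with c - 30 <= d <= c (Section 7.3.3.2; a same-day record is taken to qualify). The episode start is min(d, c) = d.

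**Reading A: the CT must fall in follow-up (c >= 0).**
- A negative start needs d < 0. Since d >= c - 30, this is possible for any CT on days 0 to 29.
- The earliest start is 0 - 30 = day -30.
- A CT on day 10 with dyspnea on day -5 qualifies and starts on day -5.
- If merging runs across index, a CT on day -14 with dyspnea on day -44 can join a CT on day 0. The merged episode then starts on day -44.

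**Reading B: the episode start must fall in follow-up (d >= 0).**
- The day -5 example drops out and no time is negative.
- Dyspnea on day 0 with a CT on any of days 0 to 30 still qualifies, at time 0.

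**How many early CTs are affected under Reading A.** Assume that the CT is uniform on days 1 to 30 and the dyspnea-to-CT lag is uniform on 0 to m days. There are 30(m + 1) pairs. The start is before index when the lag exceeds c, which gives m(m - 1)/2 pairs. It is on or before index when the lag is at least c, which gives m(m + 1)/2 pairs.

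| Assumed lag | Before index | On or before index |
|---|---|---|
| 0-3 days | 3/120 = 2.5% | 6/120 = 5.0% |
| 0-7 days | 21/240 = 8.8% | 28/240 = 11.7% |
| 0-30 days | 435/930 = 46.8% | 465/930 = 50.0% |

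The lag distributions are assumptions; the documents give none. The denominator is qualifying CTs in the first 30 days after index, not all exacerbations.

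**After the change.** If dyspnea and CT must both come after index, then d >= 1 and the smallest possible time is +1 day.

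**The case against.** The best defence is that Section 7.3 and Table 1 already confine the outcome to follow-up. An episode that by the plan's own dating rule starts on day -5 lies outside that period, so it is not an Aim 2 outcome. This is a fair reading and it removes negative times. It does not remove dyspnea coded on the day oxygen starts, because that day is part of follow-up. A time of 0 is not an error in itself; the difficulty is that the symptom which prompted oxygen can supply it.

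A second defence is that the Aim 2 analysis section is not in the public text: Section 7.2.3 refers to Section 7.6.2.2, but the visible text passes from 7.6.1.3 to 7.7. The handling of open episodes, the time origin and the matching variables could be there. This stands, and it limits the point to the visible definition.

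Third, the event also needs a CT and no claim for infection, left heart failure, embolism or another identifiable cause. That filter removes some of the deteriorations that lead to oxygen. Section 7.8 also acknowledges residual confounding in general terms.

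A reader might infer more: that oxygen patients nearly always have dyspnea coded around index, that times will be negative, and that the oxygen cohort's rate will be inflated. The documents do not support this. They give a reason for prescribing oxygen, not a coding frequency, and negative times depend on Reading A. Nor can 47% stand as the size of the problem: it rests on one assumed lag, and shorter lags give far less.

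**Conclusion.** The point holds as a gap in the visible definition. Under either reading, the deterioration that led to oxygen can be counted as an outcome of oxygen: with a start as early as day -30 if the CT governs (day -44 in the merging example), or at time 0 if the episode start governs. Two programmers could follow the text and obtain different counts and times.

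A larger effect in the oxygen cohort is plausible, because its index date is tied to a treatment given for breathlessness and a comparator's is not. It is not shown. The 2.5% to 47% range describes how often an early CT would carry a pre-index start under assumed lags. It says nothing about the difference between cohorts, which cannot be sized from the documents.

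The definition should be changed because the remedy is cheap and helps under both readings. Confidence is moderate, given the unseen Section 7.6.2.

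**What to change.** Add these rules to Section 7.3.3.2, for both cohorts alike:

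- Count an Aim 2 exacerbation only if the qualifying dyspnea and the CT are both after the index date.
- Class an episode whose first event falls on or before the index date as baseline, and report how many there are in each cohort.
- Do not apply the 14-day merging across the index date.
- State the index date as the origin for time to first exacerbation.
- Add a sensitivity analysis with a 30-day washout after index, leaving those days out of the person-years as well.

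If Section 7.6.2 already holds such a rule, a cross-reference to it is enough for that item. Dating the episode from the CT is not needed: once both components must follow index, dating onset from the first symptom is a legitimate choice.

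The cost is a few conditions in the algorithm and one extra run on data already held. The downside is that some genuine early events will be classed as baseline; the documents do not allow their number to be estimated.
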